#### **13.4 Clinical Safety Laboratory Investigations**

Not Applicable.

#### **13.5 Concomitant Medication**

The frequencies and percentages of subjects reporting concomitant medications will be tabulated overall and by vaccine group. Medications (generic drug name) will be coded using the WHO Drug dictionary (see [section 8.7](#) for definition).

## **14. INTERIM ANALYSIS**

### **14.1 Interim Analysis**

The interim analysis will be performed on serology data, i.e., serum HI titer results for all subjects through the Day 43 visit (excluding those lost to follow-up or withdrawn for other reasons), by independent individuals who are not involved in clinical study conduct or any day-to-day study activities. The unblinded results will be provided to restricted unblinded individuals only i.e., select members of Seqirus senior management not directly working on this study, who will be identified prior to the interim analysis. The unblinded results can be transmitted to HHS/BARDA prior to reporting the complete study (all subjects through day 387 post-dose). This analysis will minimally include demographic, baseline characteristics, medical history, vaccination administration, and immunogenicity (HI titer). The unblinded results will not be depicted as individual subject results; results will be presented by treatment arm only.

The interim analysis will occur after all necessary Day 43 data are available, i.e., approximately 11 months prior to reporting the complete study. The interim analysis of immunogenicity will be performed on cleaned serology data, however the snapshot of other clinical data may not be cleaned at the time of interim analysis, and will represent the final results through day 43. There are no plans to re-assay any serum samples obtained from day 1 to day 43. Day 183 immunogenicity testing will be performed separately. The lot-to-lot analysis will be performed with data from subjects in the PPS and the analyses for seroconversion and titer  $\geq 1:40$  will be performed with data from subjects in the PPS (and possibly the FAS, if the numbers of subjects between PPS and FAS differ by  $>5\%$ ) definable with the clinical data available at the time of this snapshot. The analysis performed at interim analysis will be refreshed at the final analysis on the fully cleaned and locked database.

The objective of the interim analysis is not for futility or safety concerns, hence the study will not be stopped based on the results of the interim analysis.

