7.5 Planned Analyses

A formal interim analysis of immunogenicity will be carried out by an independent statistician and programmer (to preserve the blind) after Day 43 immunogenicity data are available for all subjects (excluding those lost to follow-up or withdrawn for other reasons). No adjustments for multiplicity are needed for the interim analysis. Antibody persistence immunogenicity data (Day 183) and safety data (to Day 387) will be included in a final analysis and presented in the CSR. Further details are given in the SAP.

The final analysis will be performed when all data up to the study end (Day 387) are available. Analysis will be done on fully unblinded data by the Sponsor and all data will be presented in the final, cumulative study report.

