#### **4.2.2 Planned Unblinding for Interim Analysis**

A formal interim analysis of immunogenicity is planned when Day 43 immunogenicity data are available for all subjects (excluding those lost to follow-up or withdrawn for other reasons). To preserve the integrity of the study, the interim analysis will be handled by an independent statistician and an independent programmer from Clinical Research Organization (CRO) who are not involved in day-to-day study activities and independent from Sponsor. The unblinded protected data snapshots for interim analysis will be restricted to only unblinded individuals responsible for the interim analyses. The interim analysis results will be available to a restricted number of individuals such as select members of Sponsor senior management not directly working on this study, who will be identified prior to the interim analysis. As the results may be transmitted to the Biomedical Advanced Research and Development Authority within the Department of Health and Human Services (HHS/BARDA), Sponsor personnel engaged in discussions with HHS may also be made aware of results. No individuals with access to study results will be involved in day-to-day study activities or decisions regarding individual subject assessments. Investigators, site staff, Sponsor personnel, CRO personnel, and the serology laboratory will remain blinded to the clinical study data and subjects’ individual study arm assignment until final data from all termination visits are locked, including both individual subject serology results and serology results by group.

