### **7.4 Per Protocol Set (PPS), Immunogenicity Set**

All subjects in the FAS Immunogenicity who:

- Correctly receive the vaccine (i.e., receive the vaccine to which the subjects is randomized and at the scheduled time points).

- Have no major protocol deviations leading to exclusion (see [section 6.1](#)) as defined prior to unblinding / analysis.
- Are not excluded due to other reasons (e.g. subjects who withdrew informed consent) defined prior to unblinding or analysis (see [section 6.2](#))

In case of vaccination error, subjects in the PPS will be analyzed “as randomized” and the subject who received the wrong vaccination will be excluded from the PPS. If a subject receives a vaccine from the wrong kit number, but the same as the one the subject was randomized to, the subject will not be removed from the PPS.

Subjects randomized in the wrong stratum will be excluded from the PPS.

If a subject is unblinded during the study, except for SUSAR, he/she will be excluded from the PPS.

Similarly to FAS, PPS will also be defined per objective and timepoint:

- PPS-1 will include all subjects who are in FAS-1 and correctly received study vaccine, have no major protocol deviations leading to exclusion and are not excluded due to other reasons as defined prior to unblinding / analysis.
- PPS-2 will include all subjects who are in FAS-2 and correctly received study vaccine, have no major protocol deviations leading to exclusion and are not excluded due to other reasons as defined prior to unblinding / analysis.
- PPS-3 will include all subjects who are in FAS-3 and correctly received study vaccine, have no major protocol deviations leading to exclusion and are not excluded due to other reasons as defined prior to unblinding / analysis.

Exclusions will be considered by objective/time point, i.e., sometimes not all data of a subject but only part of the subject's data will be removed from the PPS analysis.

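### Do the protocol and SAP leave open which Day 43 run decides the co-primary objectives?

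*SAP*

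**What the plan says.** Protocol 7.5 states that "A formal interim analysis of immunogenicity will be carried out by an independent statistician and programmer" once Day 43 data are available for all subjects. It continues: "Antibody persistence immunogenicity data (Day 183) and safety data (to Day 387) will be included in a final analysis and presented in the CSR". Its next paragraph places the final analysis after all data to Day 387 are in and has all data reported there.

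SAP 14.1 describes the interim data: "The interim analysis of immunogenicity will be performed on cleaned serology data". It warns that the other clinical data in the snapshot may be uncleaned, and ends that sentence with "and will represent the final results through day 43". The next sentence says no Day 1 to Day 43 sera are to be re-assayed. Later in the section comes: "The analysis performed at interim analysis will be refreshed at the final analysis on the fully cleaned and locked database".

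On set membership, SAP 7.4 has a rule without a stated cut-off: "If a subject is unblinded during the study, except for SUSAR, he/she will be excluded from the PPS". It also says "Exclusions will be considered by objective/time point", and adds that sometimes only part of a subject's data is dropped. SAP 6.1 settles exclusions before the database is unblinded, and SAP 4.2.3 puts full unblinding after final lock. On access to interim results, SAP 4.2.2 says: "No individuals with access to study results will be involved in day-to-day study activities or decisions regarding individual subject assessments".

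**The concern.** The Day 43 co-primary tests are run twice. One sentence of SAP 14.1 appears to call the first run final, another repeats it, and neither document names the run that decides. Titers are fixed, but membership of PPS-1 (the Per Protocol Set for Day 43) is not. Cleaning of the clinical data can move subjects in or out. Taken literally, so can an event months after the Day 43 blood draw, such as a broken code.

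The stakes would be real. Lot consistency gates both the CBER co-primary objective and the pooled secondary objectives. The interim result may also go to HHS/BARDA about 11 months before the study is reported. If the two runs disagreed, a reader could argue for either, and counting a success in whichever run passed would raise the false-success rate.

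**Working it through.** **1. Do the documents point to different runs?**

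- Protocol 7.5 lists Day 183 and safety data as part of the final analysis. That wording is not exclusive, and the next paragraph has all data in the final report. It does not make the interim the deciding run.
- SAP section 1 gives the interim's purpose: immunogenicity information for health authorities planning for a possible pandemic. SAP 14.1 adds that the study will not be stopped on it.
- The word final in SAP 14.1 stands in a sentence that opens with cleaned serology and is followed by the no-re-assay statement. Read there, it means that the titers are final.
- SAP 14.1 then refreshes the analysis on locked data. An interim on a possibly uncleaned snapshot, later refreshed on the locked database, is superseded by the locked run.
- SAP 6.1 and 4.2.3 together point the same way for the exclusion list.

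The tension is therefore between two sentences of one SAP section, and context resolves it.

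**2. The plan's own figures.** Inputs from Protocol 7.4.2.3 and 7.4.2: SD 0.85, n = 718 per lot, margin 0.176 (log10 of 1.5), two-sided 95% CI, true difference 0.

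- SE = 0.85 × √(2/718) = 0.0449.
- Power of one comparison = 2Φ(0.176/0.0449 − 1.96) − 1 = 2Φ(1.963) − 1 = 95.0%. The plan says 95%.
- Overall, 0.95³ = 85.7%. The plan says about 86%.
- 718/0.90 = 797.8, so 798 recruited per lot, as stated.

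**3. How often could two runs disagree?** All three intervals lie inside the margin when the largest minus the smallest lot mean is below 0.176 − 1.96 × SE = 0.088. With 7 subjects removed per lot (n = 711) the limit is 0.0876; with 72 removed (n = 646) it is 0.083. Three lots were simulated and analysed on the full and the reduced set, with removal unrelated to titer and no covariate adjustment. There were 1,000,000 trials per setting.

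| Removed per lot | SD 0.85, ratio 1.0 | SD 0.85, ratio 1.1 | SD 0.75, ratio 1.0 | SD 0.88, ratio 1.0 |
|---|---|---|---|---|
| 1% (7) | 2.1% | 2.9% | 0.8% | 2.6% |
| 2% (14) | 3.0% | 4.1% | 1.1% | 3.8% |
| 5% (36) | 5.5% | 7.1% | 2.1% | 6.6% |
| 10% (72) | 9.1% | 11.3% | 3.8% | 10.9% |

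At SD 0.85 and ratio 1.0, the full set passes in 87.8% of trials and the reduced sets in 87.3%, 86.8%, 85.0% and 81.7%.

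A second simulation (400,000 trials per case) gave 2.1%, 3.1%, 5.5% and 9.2% for equal lots. It also shows the direction of disagreement. At 10% removal the full set passes in 87.87% of trials, the reduced set in 81.67% and at least one in 89.35%. So the full set alone passes in 89.35 − 81.67 = 7.68%, and the reduced set alone in 89.35 − 87.87 = 1.48%. Most of the disagreement at that level is lost precision.

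**4. False success.** With the extreme lots exactly at the margin, one run passes in about 2.0% of trials. If success in either run counted, the rates for 1%, 2%, 5% and 10% change are:

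- removal only: 2.3%, 2.3%, 2.5%, 2.6%;
- removals matched by additions: 2.4%, 2.5%, 2.7%, 2.9%.

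Neither document proposes an either-run rule.

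**The case for a change.** The strongest case for a change is that clarity would cost a few sentences. Neither document uses a word such as confirmatory for either run. SAP 6.1 fixes exclusions before unblinding, yet the plan has two unblindings, one for the interim and one at the end. Consent withdrawal and a broken code are also grounds for exclusion and can occur after Day 43. The phrase about objective and time point shows that time-specific exclusion was intended, but it does not say outright that later events leave PPS-1 intact. Choosing a run after seeing both would be post hoc.

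What stands is that the deciding run and the Day 43 cut-off are implied and not spelled out. What does not stand is that this leaves the result open. The refresh sentence and the interim's stated purpose favour the locked run. The part-of-the-data rule in SAP 7.4 lets a Day 43 titer be kept despite a later event. If a few late-unblinded subjects were dropped all the same, staff without access to results would make that decision, so no biased exclusion is in view. Those subjects stay in the Full Analysis Set (SAP 7.3), on which SAP 11.2 requires a supporting analysis when more than 5% are excluded from the PPS.

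**Conclusion.** No change to the plan is needed. Followed as written, the locked-database run on PPS-1 replaces the interim, one test decides, and its false-success rate is about 2.0%, below the nominal 2.5%. What is missing is detail that an analyst would supply in the same way.

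The numerical case for acting is weak. At SD 0.85 with equal lots, disagreement runs from 2.1% at 1% removal to about 9% at 10%. No document supports any turnover rate, and 718 per lot is already net of 10% dropout. Even the either-run reading moves false success only to 2.3% to 2.6% under removal, or to 2.9% at most with matched additions.

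These figures assume normal log10 titers, turnover unrelated to titer, and no covariate adjustment. The planned ANCOVA on baseline titer, age group and center may lower the residual SD; at SD 0.75 the disagreement is 0.8% to 3.8%. The conclusion also rests on the access restrictions in SAP 4.2.2 being kept, so that exclusions after the interim are made without knowledge of the results.

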#### **14.1.1 Futility Analysis**

Not Applicable.

## **15. DATA MONITORING COMMITTEES**

A data monitoring committee (DMC) will not be constituted for this study because the past studies with aH5N1 have shown no safety signals requiring monitoring by a DMC and there are planned monitoring safety procedures that can identify important safety issues on a real-time basis. Hence, there is no DMC planned in this study.

## **16. PEER REVIEW**

The type of peer review required for each output is to be identified by the study Biostatistician and Statistical Programmer (SP). Analyses/Outputs requiring statistical peer review correspond usually to the analyses of the primary and secondary objectives, and data conversion programs. Peer review of these analyses should be performed in accordance with the applicable procedures for validation of SAS programs used in clinical data analysis.

The following analyses are identified as key analyses to be peer reviewed by a biostatistician independent from the study:

- Primary immunogenicity analysis (Lot-to-lot analysis, Ratio of GMTs of two consecutive lots).

The following programs are identified as key programs to be peer reviewed by a second SP:

- Protocol deviations.
- Summary of GMTs and associated confidence interval (co-primary analysis).
- Summary and percentage of Subjects achieving HI titer of  $\geq 1:40$ , seroconversion, and associated confidence intervals (co-primary analysis).

## **17. LIST OF FINAL REPORT TABLES, LISTINGS AND FIGURES**

For the complete list of tables, listings and figures (TLFs), please refer to the post-text TLF shell document.

**18. LAYOUT SPECIFICATIONS FOR TABLES, LISTINGS AND FIGURES**

All TLFs will include a header with the following components, e.g.:

Seqirus Inc. Final Report: Study V89_18
--

Vaccine: aH5N1c Phase III, adults $\geq 18$ yr
---

The post-text TLFs shells will be created as the layouts of how tables, listings, and figures will be presented.

**20. APPENDIX A**

**20.1 Documentation of Sample Size Calculation V2.0 Dated 17Jun2014**

Biostatistics & Statistical Reporting

V89\_18

## 1 Information to enable the reproduction of the sample size

### Co- Primary Immunogenicity Objectives

To demonstrate lot-to-lot consistency across three consecutively produced lots of aH5N1c vaccine, as assessed by the ratio of geometric mean titers (GMTs) of hemagglutination inhibition (HI) antibody responses to the H5N1 vaccine strain 3 weeks after the second vaccination (day 43) in healthy adult subjects  $\geq 18$  years of age.

To evaluate immune responses to aH5N1c vaccine according to immunogenicity criteria defined by CBER recommendations 3 weeks after the second vaccine administrations (Day 43) as measured by age cohort and by strain-specific HI assays for the pooled study population of aH5N1c vaccine recipients. This evaluation will be carried out after the lot-to-lot consistency is demonstrated.

### Primary Safety Objective

To evaluate the safety and tolerability of aH5N1c vaccine and placebo in healthy adult subjects  $\geq 18$  years of age.

### 1.1 2.2 Secondary Objectives Secondary Immunogenicity Objectives

After lot-to-lot consistency is demonstrated, the aH5N1c lots will be pooled, and the following objectives assessed:

- To evaluate immune responses to aH5N1c vaccine according to immunogenicity criteria defined by CHMP recommendations (CHMP 2003, CHMP 2006) 3 weeks after the second vaccine administration (Day 43) in healthy adult subjects  $\geq 18$  years of age by age cohort\*, as measured by strain-specific HI assay.
- To evaluate immune responses to aH5N1c vaccine according to immunogenicity criteria defined by CBER and CHMP recommendations 3 weeks after the first vaccine administration (Day 22), in subjects  $\geq 18$  years of age by age cohort\*, as measured by strain-specific HI assay.
- To evaluate immune responses to aH5N1c vaccine 6 months after first vaccine administration (Day 183) in subjects ages  $\geq 18$  years of age, by age cohort, as measured by strain-specific HI assay.

\* Both CBER and CHMP criteria will be evaluated separately for each age cohort (18 to <65 years and  $\geq 65$  years, and 18 to <60 years and  $\geq 60$  years respectively).

### 1.2 Hypotheses

Primary Objectives

For lot-to-lot consistency, the following equivalence hypotheses will be tested simultaneously:

$$H_0: \quad (\mu_{\text{lot A}} - \mu_{\text{lot B}}) \leq -0.176 \text{ or } (\mu_{\text{lot A}} - \mu_{\text{lot B}}) \geq 0.176 \text{ or} \\ (\mu_{\text{lot A}} - \mu_{\text{lot C}}) \leq -0.176 \text{ or } (\mu_{\text{lot A}} - \mu_{\text{lot C}}) \geq 0.176 \text{ or} \\ (\mu_{\text{lot B}} - \mu_{\text{lot C}}) \leq -0.176 \text{ or } (\mu_{\text{lot B}} - \mu_{\text{lot C}}) \geq 0.176$$

vs.

$$H_1: \quad (\mu_{\text{lot A}} - \mu_{\text{lot B}}) > -0.176 \text{ and } (\mu_{\text{lot A}} - \mu_{\text{lot B}}) < 0.176 \text{ and} \\ (\mu_{\text{lot A}} - \mu_{\text{lot C}}) > -0.176 \text{ and } (\mu_{\text{lot A}} - \mu_{\text{lot C}}) < 0.176 \text{ and} \\ (\mu_{\text{lot B}} - \mu_{\text{lot C}}) > -0.176 \text{ and } (\mu_{\text{lot B}} - \mu_{\text{lot C}}) < 0.176$$

Here,  $H_1$  refers to the alternative hypothesis of pairwise equivalence (consistency) transformed to the log10 scale. Accordingly,  $\mu_{\text{lot A}}$ ,  $\mu_{\text{lot B}}$ , and  $\mu_{\text{lot C}}$  denote the means of log10-transformed Day 43 titers of the corresponding lot groups. The lot-to-lot consistency will be claimed if the 2-sided 95% CIs of all the three pairwise comparisons are within the equivalence ranges. Significance level to all these tests is  $\alpha = 5\%$ , which needs no adjustment for multiplicity as all hypotheses have to be rejected (intersection-union test problem).

For CBER criteria HI antibody titer  $\geq 1:40$  should meet or exceed 70% and 60% respectively for the two different age cohorts (18- <65 years of age and  $\geq 65$  years of age) the following hypothesis will be tested:

$$H_0: \quad (\pi_1 - \pi_0) \leq 0 \quad \text{vs.} \quad H_1: \quad (\pi_1 - \pi_0) > 0$$

Here,  $H_1$  refers to the alternative hypothesis.  $\pi_0$  denotes the threshold for proportion of subjects with a HI titer  $\geq 1:40$  ( $\pi_0 = 0.7$  for subjects 18 to <65 years of age and  $\pi_0 = 0.6$  for subjects  $\geq 65$  years of age). Significance levels to these tests is  $\alpha = 5\%$  which needs no adjustment for multiplicity as all hypothesis have to be rejected (intersection union problem).

### 1.3 Sample Size Calculation

#### Primary Objectives

Data observed in previous NVD studies in similar sets (V89\_04 in subjects 18-64 years of age; V89\_13 in subjects  $> 65$  years of age) showed a variability of the post vaccination titers ranging from 0.75 to 0.88 (in the log scale). With the proposed sample size, assuming a standard deviation of 0.85 for the log10 antibody titers (for each vaccine lot), approximate pairwise equivalence of factor 1 and independency, a single equivalence test based on 718 subjects per lot group has a power of 95%. The resulting overall power is approximately 86%, because the total number of comparisons is three. To account for dropouts (approximately 10%), a total of  $n=798$  per lot should be recruited.

[figure not shown]

Data observed in previous NVD studies in similar populations (V89\_04 in subjects 18-64 years of age; V89\_13 in subjects > 65 years of age) showed a proportion of 86% of subjects aged 18 to <65 years and a proportion of 81% of subjects aged 65 years and older achieving an HI antibody titer of  $\geq 1:40$ . With a sample size of 1077 evaluable subjects from the pooled lots there is an overall power of approximately 98% to achieve the CBER criteria (HI antibody titer  $\geq 1:40$  for at least 70% of the subjects aged 18 to <65 years, and for at least 60% of the subjects aged 65 years and older). To account for dropouts (approximately 10%), a minimum sample size of  $n=1197$  for all lots combined are needed.

**1.4 Software and Directories**

	Modify / delete whatever is applicable
Sample size package used	1) Nquery 2) screenshots added below
Method used, with reference (if deemed necessary)	1) Two-group t-test of equivalence of means (equal n's); One group $X^2$ test that proportion equals user specified value (normal approximation)
Historical data used:	1) Y
For manual calculation	2) V89_04, <del>V89_03</del> V89_13 corrected on 17 Jun 14 1) Not applicable

**1.5 Signature**

	1	2	3	4	5	6	7	8	9	10	11	12
Test significance levels, $\alpha$ (one-sided)	0.025	0.025	0.025	0.025	0.025	0.025	0.025	0.025	0.025	0.025	0.025	0.025
Lower equivalence limit for $\mu_1 - \mu_2, \Delta_L$	-0.176	-0.176	-0.176	-0.176	-0.176	-0.176	-0.176	-0.176	-0.176	-0.176	-0.176	-0.176
Upper equivalence limit for $\mu_1 - \mu_2, \Delta_U$	0.176	0.176	0.176	0.176	0.176	0.176	0.176	0.176	0.176	0.176	0.176	0.176
Expected difference, $\mu_1 - \mu_2$	0.000	0.000	0.000	0.000	0.000	0.000	0.041	0.041	0.041	0.041	0.041	0.041
Common standard deviation, $\sigma$	0.650	0.700	0.750	0.800	0.850	0.880	0.650	0.700	0.750	0.800	0.850	0.880
Power (%)	95	95	95	95	95	95	95	95	95	95	95	95
n per group	421	488	560	636	718	770	604	700	804	914	1032	1106

Novartis Vaccines  
Documentation of Sample Size Calculation

Confidential

Page 5  
V89\_18

One group $\chi^2$ test that proportion equals user specified value (normal approximation)						
	1	2	3	4	5	
Test significance level, $\alpha$	0,050		0,050			
1 or 2 sided test?	2		2			
Null hypothesis proportion, $\pi_0$	0,700		0,600			
Alternative proportion, $\pi_A$	0,860		0,810			
Power ( % )	99		99			
n	1077		1077			

